7.3.1 Prescribed Medications

Participants on the following concurrent prescribed medications and/or treatments will be excluded during enrollment unless they have been taken off these therapies by their general practitioner/nurse practitioner. In the latter event, the frequency of use and/or dosage may be considered by the QI on a case-by-case basis prior to recommending an appropriate washout or their enrollment in the study.

- 1. Immunomodulators (inc. corticosteroids) such as immunosuppressants or immunostimulants (4 weeks of baseline)
- 2. Cyclosporine, methotrexate, azathioprine, mycophenolate mofetil (1 week of baseline)
- 3. Antibiotics (4 weeks of baseline)

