7.4 Early Withdrawal

Personal reasons

As stated in the Informed Consent Form (ICF), a participant may withdraw from the study for any reason at any time.

Removal by Qualified Investigator

Participant discontinuation should be considered at the discretion of the Qualified Investigator. The circumstances of any discontinuation must be documented in detail in the participant file and final report. If possible, the evaluations planned for the end of study will be carried out at the time when the participant is withdrawn from the study.

Criteria for removal of participants from the study includes:

Clinical reasons

A participant may be withdrawn from the study if, in the opinion of the Qualified Investigator, it is not in the participant's best interest to continue. Any participant who experiences a serious adverse event (SAE) may be withdrawn from the study at the discretion of the Qualified Investigator. A participant will also be withdrawn due to AEs causing clinically significant illness or the need for prohibited medication(s) during the study. Any participant who becomes pregnant during the course of the study will be withdrawn and followed up with until giving birth.

Protocol violation

Any participant found to have entered this study in violation of the protocol will be discontinued from the study at the discretion of the Qualified Investigator. This will include any participant found to have been inappropriately enrolled (did not meet eligibility criteria). Participant non-compliance includes failure to show up for study visits, failure to take the investigational product as directed, or refusal to undergo study visit procedures. Participants who are found to be taking prohibited medications or supplements without the knowledge of the Qualified Investigator will also be withdrawn. Any major protocol deviations (i.e. those that increase the risk to participants and/or compromise the integrity of the study or its results) will result in participant discontinuation.

Participant Replacement

For all early withdrawals, a participant leaving the study prematurely or in the event of participant removal will NOT be replaced by unless attrition rates are high. It is understood by all concerned that an excessive rate of withdrawals can render the study un-interpretable, thus unnecessary withdrawal of participants should be avoided.

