9.7.7 Canadian Acute Respiratory Illness Flu Scale (CARIFS)

The Canadian Acute Respiratory Illness Flu Scales (CARIFS) is an 18-item questionnaire for children that assesses respiratory illness severity across three domains: symptoms, function and parental impact (**Section 16.2**). Each item is answered on a 4-point scale (no problem = 0, minor problem = 1, moderate problem = 2, major problem = 3), with a higher score denoting a more severe illness (20,21). Participants will complete the CARIFS daily throughout run-in and the study period as part of their study diary. As referenced by *Lazou Ahren et al.* (2020) and *Singh et al.* (2024), incidence, duration, and severity of cold and flu will be defined as the following (21,22):

- *Incidence* will be defined as two or more consecutive days with scores above zero (no problem) in at least two symptoms (headache, sore throat, muscle aches or pain, fever, cough, nasal congestion or runny nose, and vomiting; items 10–16) listed on the CARIFS (21).
- *Duration* will be defined as the length of time from an onset of an incidence (defined above) until the last day with symptoms followed by two days with a 0 score
- Severity will be calculated using two methods. 1) The mean total severity score per day of the individual items per incidence of cold or flu symptoms, and 2) area under the curve (AUC) of daily total symptom scores.

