10 SAFETY INSTRUCTIONS AND GUIDANCE

10.1 Adverse Events

10.1.1 Adverse Events

An adverse event (AE) is any untoward medical occurrence in a clinical investigation participant who has been administered an investigational product and does not necessarily present as having a causal relationship with this investigational product. The absence or presence of the causal relationship will be determined by the QI. An AE can be any unfavorable and unintended sign, symptom, or disease temporally associated with the use of a product, and whether or not it is considered related to that product. Pre-existing conditions that worsen during a study are to be reported as AEs and will be reviewed by the QI to provide classification.

During the study, participants should record any adverse effects in their diary. At each visit the participant will be asked, by the investigator: "Have you experienced any changes in your health since your last visit to the clinic?". Any AEs will be documented in the study record and will be classified according to the description, duration, intensity, frequency, and outcome by the medical team. The QI will assess all AEs and decide causality.

Intensity of AEs will be graded on a three-point scale (mild, moderate, severe) and reported in detail in the study record:

Mild: Awareness of event but easily tolerated

Moderate: Discomfort enough to cause some interference with usual activity

Severe: Inability to carry out usual activity

The causality relationship of investigational product to the AE will be assessed by the QI as either:

Most probable: There is a reasonable relationship between the investigational product and AEs.

The event responds to withdrawal of investigational product (dechallenge) and

recurs with rechallenge when clinically feasible.

Probable: There is a reasonable relationship between the investigational product and AEs.

The event responds to dechallenge.

Possible: There is a reasonable relationship between the investigational product and AEs.

Dechallenge information is lacking or unclear.

Unlikely: There is a temporal relationship to the investigational product administration but

there is no reasonable causal relationship between the investigational product and

the AEs.

Not related: There is no temporal relationship to investigational product administration or there

is a reasonable causal relationship between non-investigational product, concurrent

disease, or circumstance and the AEs.

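### Protocol section 7.4 makes study withdrawal compulsory for some illness-related events and offers no way to stop product and continue the diary, so primary-outcome days to Day 84 can be lost in relation to illness

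*Protocol*

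**What the plan says.** Protocol section 7.4 mixes discretionary and compulsory wording.

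- **Discretionary.** The general rule is "Participant discontinuation should be considered at the discretion of the Qualified Investigator". Best-interest and SAE withdrawals use *may*, and removal for ineligible enrolment is left to the investigator. The section closes by saying that "unnecessary withdrawal of participants should be avoided".
- **Compulsory.** Three sentences use *will*. On illness and its treatment: "A participant will also be withdrawn due to AEs causing clinically significant illness or the need for prohibited medication(s) during the study". On undisclosed products: "Participants who are found to be taking prohibited medications or supplements without the knowledge of the Qualified Investigator will also be withdrawn". On major deviations, those that raise risk or "compromise the integrity of the study or its results) will result in participant discontinuation".

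The section treats these as removals from the study. The one step that secures efficacy data is to carry out the end-of-study evaluations at the time of withdrawal, if possible. Follow-up after withdrawal is described only for pregnancy, and section 10.2 adds follow-up of AEs. No sentence separates stopping product from leaving the study.

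Sections 5 and 9.7.6 to 9.7.9 take the primary outcomes (incidence, duration and AUC) from a daily caregiver diary covering baseline to Day 84. Section 11.2 defines ITT as all randomised participants. It already excludes from PP those with deviations that affect the primary outcomes.

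**The concern.** The illness sentence lies close to the endpoint. Section 10.1.1 defines an AE broadly: "An AE can be any unfavorable and unintended sign, symptom, or disease temporally associated with the use of a product". A URTI or GITI episode can meet that definition, and section 13.3 lists worsening of such symptoms among the possible side effects. Section 13.3 also sends children whose symptoms persist or worsen to their practitioner for standard care. If that care includes a product treated as prohibited, section 7.4 requires the child to leave.

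The diary days lost would then follow illness, so the loss could be related to the outcome and could differ by arm. If the product works, more placebo children fall ill and are exposed to the rule. If product side effects cause removal, the imbalance runs the other way. An end-of-study evaluation brought forward to the withdrawal date does not supply the later diary days. A statistical analysis plan can choose how to handle missing days, but it cannot recover days that the protocol stopped collecting.

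**Working it through.** **Inputs from the protocol.** 50 children per arm; 84 days of follow-up; planned URTI episodes per child L = 1.43 (placebo) and 0.76 (active), all from section 11.1. The planned rate ratio is 0.76/1.43 = 0.531. The protocol gives no expected number of removals under section 7.4.

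**The plan's sample size.** For an effect size of 0.63: n = 2 × (1.96 + 0.8416)² / 0.63² = 39.5, so 40 per arm, and 40/(1 − 0.20) = 50. The stated 100 reproduces and is not in dispute.

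**Loss per child removed.**
- At Day 28: (84 − 28)/84 = 67% of diary days.
- At Day 56: (84 − 56)/84 = 33%.

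**Illustrative model (assumption).** Episodes follow a Poisson process at a constant rate. Each episode leads to removal with probability q, and follow-up ends at that episode. The values q = 2%, 5% and 10% are chosen for illustration.

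- Children removed per arm = 50 × (1 − exp(−qL)).
- Diary days lost per arm, of 50 × 84 = 4,200, = 4,200 × [1 − (1 − exp(−qL))/(qL)].
- Expected episodes counted per child = (1 − exp(−qL))/q. The rate ratio without an offset is therefore (1 − exp(−0.76q))/(1 − exp(−1.43q)).

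| q | Removed, placebo vs active | Days lost, placebo vs active | Rate ratio, no offset |
|---|---|---|---|
| 2% | 1.41 vs 0.75 | 59.5 vs 31.8 (1.4% vs 0.8%) | 0.535 |
| 5% | 3.45 vs 1.86 | 146.6 vs 78.8 (3.5% vs 1.9%) | 0.540 |
| 10% | 6.66 vs 3.66 | 286.5 vs 155.6 (6.8% vs 3.7%) | 0.549 |

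Placebo removals are about 1.8 to 1.9 times active removals throughout.

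**With a follow-up offset.** Mean follow-up as a fraction of 84 days is (1 − exp(−qL))/(qL). Dividing expected episodes by this gives [(1 − exp(−qL))/q] ÷ [(1 − exp(−qL))/(qL)] = L. Each arm's rate is recovered and the ratio stays at 0.531. In this model removal depends only on episodes already observed and counted.

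**Duration and AUC.** Both lose the days after removal directly. Section 11.3 compares AUC by t-test or rank-sum test, where no offset enters. A URTI episode in progress at removal also has no defined end, because section 9.7.7 runs duration "until the last day with symptoms followed by two days with a 0 score". The documents contain nothing from which to size these effects.

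**The case against.** Four points on the other side carry weight.

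**The medication trigger is partly inferred.** A reader might conclude that any child given an antibiotic or corticosteroid must leave. The text does not establish this. The entry "Antibiotics (4 weeks of baseline") stands in section 7.3.1, a list for exclusion at enrolment with washouts before baseline. The explicit on-study restriction is in section 7.3.2 and concerns OTC products and supplements. Section 13.3 allows OTC fever and cough medicine and mentions standard care without mentioning withdrawal. Reading the 7.3.1 list as the on-study list is plausible, but no more than that.

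**Ordinary colds are not the trigger.** A reader might also infer that each URTI episode risks removal. The sentence requires a clinically significant illness or a need for prohibited medication, and the investigator assesses AEs. A trial planned around 1.43 episodes per placebo child cannot sensibly mean to remove children for routine episodes.

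**The outcome link is shown for one sentence only.** No such mechanism is shown for major deviations. The undisclosed-product route is narrow, because the diary records concomitant products daily. The ineligible-enrolment sentence is already discretionary and is not part of the defect.

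**Some of the loss is not specific to section 7.4.** Any dropout, or an episode still running at Day 84, also lacks the two closing zero days. How to treat these, and whether to use an offset, can be settled in a statistical analysis plan.

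These points limit the reach and size of the concern. They do not remove the compulsory wording, which the general discretion sentence contradicts without overriding, and they supply no route for continuing the diary.

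**Conclusion.** The point holds at low severity. Section 7.4 requires study withdrawal in three situations despite its discretion sentence. One of these can coincide with the illness being measured, and the protocol stops the diary when it occurs. Primary-outcome days can therefore be lost, in relation to outcome, from children whom section 11.2 keeps in ITT.

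The size rests on an assumed 2% to 10% removal per URTI episode and a constant Poisson rate. On that basis the bias in URTI incidence is small and towards no effect: the ratio goes from 0.531 to between 0.535 and 0.549 without an offset, with no change with one. AUC and duration are the main exposure and remain unquantified.

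Two stronger conclusions are tempting. The documents do not support the claim that the rule would materially distort the incidence result, since they give no removal rate and the illustration shows little movement. Nor do they support a claim that the fix would raise power: children who stop product and lose its effect dilute the ITT difference, so retaining them cannot be counted as a gain.

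**What to change.** In section 7.4, amend the illness and prohibited-medication sentence and, for consistency, the undisclosed-product and major-deviation sentences. Suggested text:

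*In these situations the Qualified Investigator may stop investigational product, and must stop it where continuing would add risk to the child. The daily diary and remaining scheduled visits continue to Day 84 unless consent or assent is withdrawn or the Qualified Investigator judges that further follow-up is not in the child's interest. All data collected are included in ITT; deviations affecting primary outcomes are handled through the PP definition.*

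Leave the ineligible-enrolment, best-interest, SAE and pregnancy sentences as they are. Removal is not needed to keep PP clean, because section 11.2 already excludes such deviations.

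**Cost.** No new visits or instruments are needed: the diary exists and Visits 3 and 4 are already remote. Some ITT children will be off product or taking a prohibited one, which dilutes the estimate in proportion to their number. Their families keep the diary burden to Day 84. The change needs a documented amendment, possibly with IRB and Health Canada review (sections 9.11 and 11.5), and the consent form may need revising to describe follow-up after product is stopped.

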8 INVESTIGATIONAL PRODUCT

8.1 Manufacturing and Storage

The investigational product will be provided to KGK Science Inc. by the Sponsor. The investigational product will be carefully stored at the study site in a lockable, limited access area, accessible only to study team personnel in compliance with pertinent regulations. Only authorized persons will have access to the investigational product. The products will be stored as per storage conditions on the label and will not be exposed to direct sunlight or heat. The investigational products will be kept in a locked investigational product storage room at KGK Science Inc. on receipt. An accountability log will be kept for the investigational products.

All unused investigational product will be returned to the study Sponsor by KGK Science Inc. (at the Sponsor's expense) or destroyed on receipt of written confirmation from the Sponsor at study closeout (within one month of the last participant's last visit).

Manufactured by:

Genomelabs Bio Pvt Ltd.

[name]

8.2 Labelling and Coding

The investigational product will be labeled according to the requirements of ICH-GCP guidelines and applicable local regulatory guidelines. Investigational product will be randomized and coded by an unblinded person at KGK who is not involved in data collection or analysis.

8.3 Investigational Product (Bacillus coagulans SNZ 1969)

Medicinal Ingredient	Quantity (per dose)
Bacillus coagulans SNZ 1969	1 Billion CFU/g

Non-medicinal ingredients: Glucidex (maltodextrin), Magnesium stearate, Banana dry mix flavour.

8.4 Placebo

Ingredients: Glucidex (Maltodextrin), Magnesium Stearate, Banana dry mix flavour.

8.5 Directions

Participants will be instructed to fully consume 1 sachet completely dissolved in approximately 50 ml of water before breakfast starting on Day 1 and throughout the duration of the study. If after consuming the dose residual powder remains in the cup add more water to dissolve remaining powder and consume remaining product. Clinic staff will instruct participants to save all unused and open packages and return them to KGK Science Inc. for a determination of compliance. If a dose is missed participants are instructed

to take it as soon as they remember on the same day or the next day. Participants will be advised not to exceed 2 sachets daily.

8.6 Rescue Medication

Rescue medication is not applicable for this study

8.7 Randomization

Each participant will be assigned a randomization code according to the order of the randomization list generated. Enrolled participants will be randomized to the different study arms at Day 0.

Block randomization will be implemented for this study. It is a method that helps to reduce bias and achieve balance in the allocation of participants to study arms. This technique helps to increase the probability that each arm will contain an equal number of individuals by sequencing participant assignments by blocks. Participants are randomized within blocks so that an equal number are assigned to each study arm. Allocation proceeds by randomly selecting one ordering and assigning the next block of participants to a study group based on a specified sequence. The block size needs to be divisible by the number of study groups (19).

8.8 Blinding and Allocation Concealment

Concealment of the allocation of study arms will be employed using a secure document located on Microsoft SharePoint. Information regarding the study arm associated with each randomization number will be readily available for the Qualified Investigator to access in the event that it becomes necessary to know which product a participant is taking for the sake of the participant's health care.

Unblinding should not occur except in the case of emergency situations. If a SAE occurs, for which the identity of the investigational product administered is necessary to manage the participant's condition, the study arm assigned to the participant will be unblinded and the investigational product identified. The Sponsor must be notified of any unblinding within 24 hours. Details of participants who are unblinded during the study will be included in the Final Report.

9 STUDY ASSESSMENTS

9.1 Screening (Day -45 to Day -15; Visit 1)*

* At the discretion of the Qualified Investigator, any participants falling outside of the screening window (Day -45 to Day -15) due to scheduling issues will be asked to repeat eligibility/screening procedures prior to randomization at baseline.

At screening, an ICF will be given to the potential volunteer. They will be required to read the information and will be given the opportunity to seek more information if needed or provided with the option of taking the consent form home to review prior to making their decision. If agreeable, the caregiver and volunteer will sign the consent and assent forms as applicable and receive a duplicate of the signed copy. Once consent has been obtained, screening will proceed. Each volunteer will be assigned a screening number to be entered in the screening and enrollment log.

Screening assessments include:

- 1. Review medical history, concomitant therapies (inclusive of previous vaccinations), and current health status
- 2. Assess inclusion and exclusion criteria
- 3. Review any pre-emergent AEs
- 4. Urine pregnancy test for potential volunteers that are of child-bearing potential
- 5. Seated resting BP and HR measurements (see Section 9.7.2)
- 6. Weight and height measurements (see Section 9.7.1)
- 7. Dispense study diary inclusive of the CARIFS questionnaire, Additional respiratory tract symptoms questionnaire, and GITI Symptom Questionnaire and instruct participants on completion (see Section 9.7.6)
- 8. Dispense saliva collection kit and instruct participants on use (See Section 9.7.5)
- 9. Dispense stool collection kit and instruct participants on use (see Section 9.7.4)

The next appointment will be scheduled for potentially eligible volunteers for their baseline visit.

9.2 Run-in (Day -14 to Day -1)

Participants will complete the study diary inclusive of the CARIFS, Additional respiratory tract symptoms, and GITI symptoms questionnaires during the 14-day run-in period.

9.3 Day 0 (Baseline, Visit 2)

Eligible volunteers will return to the clinic for baseline assessments with collected stool and saliva samples.

Baseline (Day 0) assessments include:

- 1. Review concomitant therapies (inclusive of previous vaccinations) and current health status
- 2. Assess inclusion and exclusion criteria
- 3. Review any pre-emergent AEs
- 4. Urine pregnancy test for potential volunteers that are of child-bearing potential
- 5. Vital sign measurements (BP and HR)
- 6. Weight and height measurements

- 7. Randomization of eligible participants
- 8. Collect blood samples for analysis of: (see Section 9.7.3)
 - a. Quantibody® Human Immune Response Array
 - b. Immunoglobulins A (IgA), G (IgG), E (IgE) and M (IgM) serum levels
- 9. Collect saliva sample for the analysis of Salivary Ig A Levels
- 10. Collect stool samples for microbiome analysis
- 11. Review completed study diaries including CARIFS, Additional respiratory tract symptoms, and GITI symptoms questionnaires
- 12. Dispense investigational product and instruct participants on use
- 13. Dispense study diary inclusive of the CARIFS, Additional respiratory tract symptoms, and GITI symptoms questionnaires
- 14. Dispense stool collection kit for microbiome analysis for Visit 5 (End of Study visit)
- 15. Dispense saliva collection kit for Visit 5 (End of Study visit)

The next visit will be conducted remotely and scheduled for Day 28 (\pm 2 days)

9.4 Visit 3 (Day 28 ± 2 days)

Participants will attend remotely for Visit 3 assessments with completed study diaries inclusive of the CARIFS, Additional respiratory tract symptoms, and GITI symptoms questionnaires.

Visit 3 assessments include:

- 1. Review compliance by referencing study diaries and participant/caregiver count of study product
- 2. Review completed study diaries including CARIFS, Additional respiratory tract symptoms, and GITI symptoms questionnaires
- 3. Review concomitant therapies and AEs
- 4. Dispense new study diary

The next visit will be conducted remotely and scheduled for Day 56 (\pm 2 days).

